## 11.5 POOLABILITY

Subject baseline risk will be statistically compared between centers and regions (i.e. United States vs. OUS). Chi-square tests will be used to compare categorical risk factors while analysis of variance will be used to compare continuous risk factors. Comparisons will be based on the following demographic and pre-operative variables: age, sex, etiology, previous heart valve replacement surgery, valvular lesion, pre-operative NYHA, concomitant cardiac procedures, and coexisting cardiovascular conditions. Also included in the analysis will be the size of implant. Furthermore, time to event for the following events will be compared between centers via a log-rank statistic: thromboembolism, all hemorrhage, death or explant, and death. Additional analyses may be performed if the need arises.

## 11.6 MISSING DATA

All statistical tests on the effectiveness endpoints will be performed in two ways: (1) using only those subjects with available required for endpoint analysis and (2) by using the method of last observation carried forward (LOCF). Both methods of analyses will then be compared. However, both methods will be used for the comparison of NYHA classification at 8 year post implant to OPC (75%) and for the comparison of hemodynamic performance one year to baseline for the purpose of investigating the effect of loss-to-follow-up.

NYHA classification and hemodynamic performance will be summarized at each of the follow-up interval. In addition, the NYHA classification will only be statistically compared to OPC at 8 years post implant and only the one year post implant hemodynamic performance will be statistically compared to baseline.

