where  $p$  is the proportion of the subjects in NYHA Class I or Class II at 8 years post implant. The expected proportion of the alive subjects in NYHA class I or II at eight years is above 90%, based on 8 year follow up data for the Carpentier-Edwards PERIMOUNT 2700/2800/2900 valve (this proportion is above 90% within the subjects with valid NYHA assessment at each annual visit till 8 years follow up). Based on this expected proportion, a sample size of 45 subjects provides 85% power to test the hypothesis that the true proportion is greater than 75% using an exact binomial test. Thus, the sample size of 101 subjects with NYHA data at 8 year post implant is more than adequate to provide sufficient power.

The calculated number of subjects ( $n$ ) that must be enrolled in order to have 101 subjects survive to 8 years post implant with 99% probability is based on the binomial distribution. Specifically,  $n$  is such that

$$1 - \sum_{x=1}^{101} \binom{n}{x} p^x (1-p)^{n-x} > 99\%$$

where  $p$  is the probability that a subject will survive for 8 years post implant. This calculation can be performed using standard statistical software. Based on the reported 8-year survival of 60% from Aupart, et al. (2006) [8], a sample size of 195 subjects fulfills the requirements of the equation above. Based on the data collected in a previous post approval study conducted by

---

PROPRIETARY DATA: This document and the information contained herein may not be reproduced, used or disclosed without written permission from Edwards Lifesciences LLC.

Edwards (Study 98-1), a lost to follow-up rate of 7.8% was observed among subjects who reached 5 or more years of follow-up post implant. The sample size is further inflated to 225 to account for up to a 15% rate of lost to follow up.

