## **11.4 EFFECTIVENESS ANALYSIS**

### **Subject functional classification**

Subjects will be stratified according to the NYHA classification preoperatively, at 6 months and annually post implant for 8 years. The distribution (numbers of subjects and percentages) in the various NYHA classes will be tabulated at each follow-up interval.

The primary effectiveness analysis will include all the subjects who survived the implant procedure and have at least one post-implant NYHA assessment. The proportion of the subjects in NYHA Classes I and II at 8 years post implant will be calculated to determine if it is  $\geq 75\%$  using a one-sided Binomial exact test. For subjects who die, withdraw or are lost to follow-up before reaching the 8 year follow-up visit, the last observed NYHA classes will be used in this analysis. As a consequence, those subjects will be counted as failures if they were in NYHA Classes III or IV at the time those events occurred. Subjects whose status at the time of the events is not known will be counted as failures if they were in NYHA Classes III or IV during their last assessment prior to the time of the events.

The proportion of subjects in NYHA Classes I and II and proportion of subjects who died and were in NYHA Classes III and IV at death or at their last known NYHA classification will also be calculated at each annual report.

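### The available-case versus LOCF comparison in Section 11.6 cannot isolate the effect of loss to follow-up on 8-year NYHA class, and cannot detect worsening after a lost subject's last visit

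*Combined protocol and SAP*

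**What the plan says.** Section 11.6 performs the effectiveness tests in two ways, on subjects with the required data and with LOCF, and compares the results. For the 8-year NYHA test against 75%, and for one-year hemodynamics against baseline, it gives the reason as "for the purpose of investigating the effect of loss-to-follow-up".

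Section 11.4 defines the NYHA carry-forward. It applies to three groups together: "For subjects who die, withdraw or are lost to follow-up before reaching the 8 year follow-up visit". Each keeps the last class observed and counts as a failure only if that class was III or IV. Sections 11.2 and 11.4 restrict the set to subjects with at least one post-implant NYHA assessment. Section 11.4 also tabulates, at each annual report, the proportion who died and were last in Class III or IV.

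Section 11.1 supplies the planning figures: 60% survival at 8 years, an earlier study in which "a lost to follow-up rate of 7.8% was observed among subjects who reached 5 or more years of follow-up post implant", and an increase to 225 subjects "to account for up to a 15% rate of lost to follow up".

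**The concern.** The two runs differ by every subject who has a post-implant reading but no 8-year reading. That group mixes deaths with subjects lost alive, and on the plan's own survival figure deaths are the larger part. A gap between the runs may therefore reflect the last class of those who died and have nothing to do with loss.

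For subjects lost alive, LOCF inserts a class recorded before they were lost. Deterioration after that point cannot enter either run. The main worry about loss, that people who stop attending do worse afterwards, is the one thing the comparison cannot register.

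No other sensitivity analysis for missing data is planned on the primary effectiveness endpoint. A gap could be taken for a loss effect when there is none, and agreement could give comfort that the data do not support.

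**Working it through.** **Plan's own figures.** With 60% survival, P(at least 101 survivors) is 0.9917 for n = 195 and 0.9896 for n = 194, so 195 reproduces. 195 × 1.15 = 224.25, which gives 225. For the NYHA test with n = 45, the one-sided exact rule is at least 39 in Class I/II: alpha 0.045, power 0.841 at 90%, close to the stated 85%.

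**Who separates the runs.** Inputs from 11.1: N = 225, survival 60%, loss 7.8% or 15%. Assumption: loss is counted on all 225, and 40% of the rest die.
- 7.8%: lost = 0.078 × 225 = 17.55; deaths = 0.40 × (225 − 17.55) = 82.98; deaths' share = 82.98 / 100.53 = 83%.
- 15%: lost = 0.15 × 225 = 33.75; deaths = 0.40 × (225 − 33.75) = 76.5; deaths' share = 76.5 / 110.25 = 69%.

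Deaths before any NYHA reading are outside the LOCF set, and the documents give no count. Removing 8 (assumed) lowers the shares to 74.98 / 92.53 = 81% and 68.5 / 102.25 = 67%. At 15% loss, about 43 deaths (76.5 − 33.75) would have to precede the first reading before losses equalled deaths.

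**A gap with no loss effect.** Assume completers are 90% Class I/II, lost subjects the same, and deaths last seen at 90%, 75% or 60%. Then available-case minus LOCF = (0.90 − deaths' share in I/II) × deaths / 225.

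| Completers / deaths / lost | Deaths 90% | Deaths 75% | Deaths 60% |
|---|---|---|---|
| 124 / 83 / 18 | 0 | 5.5 points | 11.1 points |
| 115 / 76 / 34 | 0 | 5.1 points | 10.1 points |

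**A loss effect with no trace.** Assume completers are 92% Class I/II, and test the living (completers plus lost) against 75% with the one-sided exact test at 0.05. The loss counts are illustrative.
- 115 completers (106 in I/II) and 27 lost, which is 27 / 225 = 12%. There are 142 living, and at least 116 must be in I/II.
  - 17 of 27 in III/IV: 116/142, p = 0.037, passes.
  - 18 of 27: 115/142, p = 0.057, fails.
  - All 27: 106/142 = 74.6%, p = 0.58.
- 125 completers (115 in I/II) and 14 lost, which is 14 / 225 = 6.2%. All 14 in III/IV: 115/139 = 82.7%, p = 0.02, still passes.

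In each case the planned available-case and LOCF results are the same whatever the true 8-year class of the lost subjects. The available-case test on 106/115 alone gives p < 0.0001.

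**The case against.** The comparison is not empty. It does reflect whether lost subjects' last recorded class differed from that of completers, though mixed with the deaths. A reader might infer that it says nothing about loss; the documents do not support that.

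The annual tabulation in 11.4 of deaths in Class III/IV gives much of the information needed to describe the deaths' contribution. That stands, but the table is descriptive. It does not put the two runs on the same footing and does not touch living lost subjects.

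Loss may also turn out small. With 14 lost in the illustration the conclusion survives the worst case, and with 27 it takes two-thirds of them in Class III/IV to overturn it, against the more than 90% in Class I/II that 11.1 expects among the living. This limits the likely consequence but does not make the comparison fit its stated purpose.

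Finally, 11.6 sets no rule for interpreting agreement or disagreement, so it cannot be said that the sponsor will misreport either.

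**Conclusion.** The point holds for the 8-year NYHA comparison. The planned contrast cannot separate loss from death, and it cannot detect worsening after the last visit. On the plan's survival and loss figures, deaths are about 69% to 83% of the subjects separating the runs, somewhat less once deaths before any reading are removed. The gap they produce alone is 0 to about 11 points over the assumed range for their last class.

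Three stronger readings are tempting but unsupported:
- That LOCF adds everyone who died. It adds only those with a post-implant reading.
- That both runs would agree at the completers' 92% if lost subjects deteriorated. That also needs deaths to have been last seen at about 92%. What holds generally is that later deterioration moves neither run.
- That the planned loss would overturn the effectiveness result. All lost subjects in Class III/IV is a bound, not a forecast.

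Section 11.6 also names one-year hemodynamics, but the documents give no one-year death or loss figure, so no size is claimed there. Withdrawals and explants have no stated rate and are not in the counts.

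**What to change.** For 8-year NYHA, in Section 11.6:
1. Handle deaths identically in both runs by the 11.4 rule, so that the runs differ only in living subjects without an 8-year reading: lost, withdrawn, exited after explant, or missed visit.
2. Add one bounding run that counts these living subjects as not in Class I/II, and report how many of them would have to be in Class III/IV for the 75% test to fail. With deaths included, that count will depend on the deaths' last class, so it will not equal the 18 of 27 shown for the living alone.
3. Label the existing available-case versus LOCF contrast as the combined effect of death and loss.

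The cost is SAP wording and two extra runs on data already collected. The primary analysis in 11.4 is unchanged. The downside is a bounding figure that will look less favourable than the primary result.

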## 12. ETHICAL AND REGULATORY CONSIDERATIONS

The following must be observed in order to comply with the sponsor's policy for conduct and monitoring of clinical investigations; they also represent sound research practice.

A written subject informed consent form will be obtained preoperatively from all subjects. The subject must be adequately informed of his or her participation in the clinical study and what will be required of him or her in order to comply with the protocol requirements. In addition, a subject informed consent form is required to allow appropriate data collection and data monitoring including access to medical records by the sponsor and regulatory agencies [REDACTED].

If an Institutional Review Board (IRB) or Ethics Committee (EC) exists for an institution, this board/committee must approve the subject informed consent form and protocol for use at its institution. A written statement by the IRB / EC indicating approval of the subject informed consent form and protocol must be submitted to the sponsor prior to study initiation.

### **13. HEALTH ECONOMIC INFORMATION**

In the United States only, the Sponsor may choose to obtain billing information such as charges associated with the Intensive Care Unit (ICU) and hospital stays to evaluate hospital costs for the initial implant hospitalization and subsequent readmissions, as necessary. For each subject, hospital charge data will be obtained from form UB-04 or similar report provided by the hospital.

### **14. CASE REPORT FORMS**

CRFs for individual subjects will be provided by Edwards [REDACTED]. The principal investigator or designee must keep a separate log of subject names and current addresses to facilitate record keeping and his or her ability to contact subjects for future follow-up.

CRFs are used to record study data and are an integral part of the study and subsequent reports. Therefore, the reports must be legible and complete. In order to comply with the HIPAA regulations and European data protection laws, any information related to the subject's identity must be redacted. All forms should be filled out using a ballpoint pen. Errors should be corrected by drawing a single strikethrough in ink, initialed and dated by the person who makes the change on the day the change is made. Copies of the changed form must be provided to the sponsor and retained in the subject study file.

A CRF must be completed and signed by the principal investigator, co-investigator or his or her designee listed in the Delegation of Authority form for each subject receiving a study valve, including subjects withdrawn from the study for any reason. The reason for withdrawal must be noted on the CRF, by the investigator.

Since there is a potential for errors, inaccuracies, and illegibility in transcribing data onto CRFs, originals or photocopies of all relevant operative records and reports, postoperative examinations, laboratory and other test results must be kept on file. CRFs and copies of test results must be available at all times for inspection by the study sponsor, the study monitor, and authorized regulatory bodies.

CRF's must be kept current to reflect subject status at each phase during the course of the study. Instructions for CRF collection or submission are provided in the CRF synopsis.

Electronic data capture (EDC) may be used for part or all of the data collection in this study. Edwards will provide training in the use of EDC to all necessary site personnel. Each investigator and staff participant will be assigned a unique password and only that individual should access subject records under that password. Changes made to the electronic record after a report has been saved or "committed" will be tracked in an electronic audit file linked to the date the change was made and the password of the individual who opened the record. Regardless of the type of CRF used, the sponsor will monitor subject CRFs for agreement with source documents on an ongoing basis.

## **15. STUDY TERMINATION**

The principal investigator will be notified in writing upon termination of the study. Edwards retains the right to suspend or terminate this clinical investigation at any time.

## **16. RECORD RETENTION**

Study files must be maintained at the clinical site for a minimum of two years after the study is either completed or terminated or until Edwards notifies the investigator that the records may be destroyed or in accordance with country specific regulations.

## **17. STUDY RESPONSIBILITIES**

### **17.1 INVESTIGATOR RESPONSIBILITIES**

The principal investigator is responsible for obtaining IRB/EC approval for the study at his or her institution.

Study records including CRFs, signed Agreement, originals of all blood and hemodynamic studies, signed informed consents, a copy of the implant data card, IRB/EC approval letters, the log of IRB/EC submissions, and other documents pertaining to the conduct of the study should be kept on file by the investigator.

The investigator(s) will adhere to the regulations that provide the greatest protection to the subject. The investigator is responsible to comply with the following regulations:

US Code of Federal Regulations:

- 21 CFR part 50: Protection of Human Subjects
- 21 CFR part 54: Financial Disclosure
- 21 CFR part 56: Institutional Review Boards
- 21 CFR part 814, subpart E: Post Approval Requirements

In Europe, EU Medical Device Vigilance System

and the:

- ICH Good Clinical Practice Guidelines
- Declaration of Helsinki
- US Department of Health and Human Services: Health Insurance Portability and Accountability Act of 1996 (HIPAA)
- Local and Regional Laws of the Country including Data Protection and ISO 14155 Part 1 and 2: 2003 Clinical Investigation of Medical Devices for Human Subjects, where appropriate for commercially available products

All protocol deviations must be fully documented and explained on the CRF. These include noncompliance related to inclusion/exclusion criteria, consent form, blood data, echo and follow-up visits.

Although the risks to the subject are felt to be the same as those reported for other available bioprostheses, the subjects receiving the Magna Ease valve will be closely followed. Any unusual or unanticipated adverse events will be reported immediately to the sponsor (see 10.1) and if applicable, to the IRB/EC as outlined in the Investigator's Statement and Agreement. If deemed necessary by the investigator, the IRB/EC, or the sponsor, the investigation may be suspended pending a thorough study of the incident.

If the investigator wishes to assign the files to someone else or move them to another location, he or she should consult with the sponsor in writing as to this change. If there is a change or addition of co-investigators, an amended agreement must be completed promptly. Any other personnel changes should be reported immediately to the monitor and a training program scheduled.

Monitoring visits will be scheduled throughout the course of the study. It is essential that the investigator set aside a sufficient amount of time for these visits to permit an adequate review of the study's progress, completed CRFs and original records.

## 17.2 SPONSOR/ STUDY MONITOR RESPONSIBILITIES

A study monitor assigned to the study by the sponsor will monitor the progress of the study. The study monitor must be acquainted with the investigator and other key people involved in the study. The study monitor will remain in close contact with the site throughout the duration of the study to answer any questions and provide any needed materials, e.g. CRFs.

The study monitor will be responsible for monitoring CRFs and visiting the site periodically to monitor study progress and compliance with the study protocol. The local data protection laws will be followed. Monitoring visits will be scheduled throughout the duration of the study at a mutually convenient time for the monitor and principal investigator or designee.

The sponsor will provide results of the ongoing study to the Food and Drug Administration, including a comparison to the available data in the heart valve literature regarding other FDA-approved bioprosthetic valves implanted in the aortic position. An Interim Post-Approval Study Status Report will be submitted every 6 months during the first two years of the study and annually thereafter. A Final Clinical Study Report will be prepared as early as 3 months after the last study subject completes follow-up.

## 17.3 STUDY CHANGES

Changes in the protocol may be made only by written amendment submitted to and agreed upon by FDA. Following written approval of a protocol amendment by FDA, the sponsor will submit the amended protocol and associated document to the IRB/EC. The above changes shall be implemented upon written approval by the respective IRB/EC. Administrative changes may be communicated to FDA and to the IRB/EC via the Annual Report.

## 17.4 IMPLANT DATA CARD

After implantation, subjects will be given the Implant Data Card by the Investigator prior to discharge [REDACTED]. This identification card allows subjects to inform healthcare providers what type of implant they have when they seek care.

## 17.5 STUDY PUBLICATION

Investigators shall submit to Edwards early drafts of all abstracts, manuscripts or presentations authored by investigators and collaborators based on data generated from the clinical study at least sixty days prior to submission of the abstract, manuscript for publication or presentation. Edwards shall have the right to advise investigators regarding proprietary information which shall not be divulged or the patentability of any inventions disclosed in the manuscripts. If requested by Edwards, investigators shall delay submission of manuscripts for publication up to ninety days to permit preparation and filing of related patent applications. In addition, Edwards shall have the right to require that any publication concerning the work performed hereunder acknowledges Edwards' financial support.

It is understood, however, that no press releases, literature, advertising, publicity, or written statements in connection with work under the Clinical Studies Agreement having or containing any reference to Edwards shall be made by the clinical site and/or the investigator without the prior written consent of Edwards. The clinical site and the investigator reserve the right to acknowledge the source of sponsorship in response to any legitimate inquiry.

Neither party will use the name of the other in any form of advertising or publicity without the written permission of the other party.

